In the event that a patient experiences a moderate infusion-related event (NCI CTCAE Grade 2) or flushing, fever, or throat pain, the patient should have his or her infusion immediately interrupted and should receive aggressive symptomatic treatment (e.g. oral or i.v. antihistamine, anti-pyretic, glucocorticoids, epinephrine, bronchodilators, oxygen). The infusion should be restarted only after the symptoms have adequately resolved to baseline grade. The infusion rate at restart should be half of the infusion rate that was in progress at the time of the onset of the infusion-related event. For the subsequent infusion, administer oral premedication with antihistamine and anti-pyretic and monitor closely for infusion-related reactions.

For severe or life-threatening infusion-related events (NCI CTCAE Grade 3 or 4), the infusion should be stopped immediately, and aggressive resuscitation and supportive measures should be initiated (administer aggressive symptomatic treatment e.g. oral or i.v. antihistamine, antipyretic, glucocorticoids, epinephrine, bronchodilators, oxygen). Patients experiencing severe or life-threatening infusion-related events will not receive further infusion and will be further managed as clinically indicated until the event resolves.

As per the IB withhold atezolizumab for any of the following:

- Grade 2 pneumonitis
- Aspartate aminotransferase (AST) or alanine aminotransferase (ALT) greater than 3 and up to 5 times upper limit of normal (ULN) or total bilirubin greater than 1.5 and up to 3 times ULN
- Grade 2 or 3 diarrhea or colitis
- Grade 2 or 3 hypophysitis
- Symptomatic adrenal insufficiency,
- Grade 3 or 4 hypothyroidism or hyperthyroidism

23 MAY 2023 Version 6.0 Page: 64 of 181

- Grade 3 or 4 hyperglycemia
- Suspected Stevens-Johnson syndrome (SJS) or toxic epidermal necrolysis (TEN)
- Grade 2 immune-mediated neuropathy, including facial paresis
- Grade 2 ocular inflammatory toxicity
- Grade 2 or 3 pancreatitis, or Grade 3 or 4 increases in amylase or lipase levels (greater than 2.0 times ULN)
- Grade 3 or 4 infection
- Grade 2 infusion-related reactions
- Grade 3 rash
- Grade 1 immune-mediated pericarditis
- Grade 2 immune-related nephritis
- Grade 2 or 3 immune-related myositis

Atezolizumab may be resumed in patients whose adverse reactions recover to Grade 0–1 (except for Grade 1 immune-mediated pericarditis).

Permanently discontinue atezolizumab for any of the following:

- Grade 3 or 4 pneumonitis

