Atezolizumab may be withheld for a period of time beyond 12 weeks to allow for corticosteroids to be reduced to ≤ 10 mg/day oral prednisone or equivalent. The acceptable length of the extended period of time must be agreed upon by the investigator and the sponsor. Recurrent Grade 2 immune-mediated adverse events may also mandate skipping a dose of atezolizumab or the use of steroids. Consideration for benefit-risk balance should be made by the investigator, with consideration of the totality of information as it pertains to the nature of the toxicity and the degree of clinical benefit a given patient may be experiencing prior to further administration of atezolizumab.

Atezolizumab should be permanently discontinued in patients with life-threatening immunemediated adverse events. However, resumption of atezolizumab may be considered in patients who are deriving benefit and have fully recovered from the immune-related event. Patients can be rechallenged with atezolizumab only after approval has been documented by both the investigator (or an appropriate delegate) and the sponsor.

Management of immune-mediated AEs

For further details, please also refer to the latest version of the investigator's brochure of atezolizumab.

Immune-mediated pneumonitis or interstitial lung disease

Immune-mediated pneumonitis or interstitial lung disease, defined as requiring use of corticosteroids and with no clear alternate etiology, might occur during treatment with atezolizumab. Refer to the latest available version of atezolizumab IB for further details. It is

23 MAY 2023 Version 6.0 Page: 66 of 181

recommended to monitor patients for signs or symptoms of pneumonitis (dyspnea, cough, fatigue, hypoxia) with radiographic imaging.

All pulmonary events should be thoroughly evaluated for other commonly reported etiologies such as pneumonia or other infection, lymphangitic carcinomatosis, pulmonary embolism, heart failure, chronic obstructive pulmonary disease, or pulmonary hypertension. COVID-19 evaluation should be performed per institutional guidelines where relevant.

The management of immune-mediated pneumonitis will be according to the severity (Table 7–6).

Table 7–6: Management guidelines for pulmonary events, including pneumonitis

Event	CTCAE Grade 1	CTCAE Grade 2	CTCAE Grade 3 or 4
Pulmonary event	Continue atezolizumab and monitor closely	Withhold atezolizumab until resolution	Permanently discontinue atezolizumab and contact sponsor ^c

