	Re-evaluate on serial imaging	Refer patient to pulmonary and infectious disease specialist and consider	Oral or i.v. broad-spectrum
	Consider patient referral to pulmonary specialist	bronchoscopy or BAL with or without transbronchial biopsy	administered in parallel to the immunosuppressive treatment
	For recurrent events, treat as a Grade 3 or 4 event	Initiate treatment with 1–2 mg/kg/day oral prednisone or equivalent	Bronchoscopy or BAL with or without transbronchial biopsy is recommended
		Resume atezolizumab if event resolves to ≤ Grade 1 within 12 weeks	Initiate treatment with 1–2 mg/kg/day i.v. methylprednisone
		Permanently discontinue atezolizumab if event does not resolve to ≤ Grade 1 within 12 weeks and contact the sponsor ^{a, b, c, d}	If event does not improve within 48 hours after initiating corticosteroids, consider adding an immunosuppressive agent
		For recurrent events or events with no improvement after 48–72 hours of corticosteroids, treat as a Grade 3 or 4 event	If event resolves to Grade 1 or better, taper corticosteroids over ≥ 1 month

BAL = bronchoscopic alveolar lavage; CTCAE = Common Terminology Criteria for Adverse Events; i.v. = intravenous.

a: If corticosteroids have been initiated, they must be tapered over ≥ 1 month to ≤ 10 mg/day oral prednisone or equivalent before atezolizumab can be resumed.

b: Atezolizumab may be withheld for a period of time beyond 12 weeks to allow for corticosteroids to be reduced to ≤ 10 mg/day oral prednisone or equivalent. The acceptable length of the extended period of time must be agreed upon by the investigator and the sponsor.

c: Resumption of atezolizumab may be considered in patients who are deriving benefit and have fully recovered from the immune-related event. Patients can be rechallenged with atezolizumab only after approval has been documented by both the investigator (or an appropriate delegate) and the sponsor.

d: In case of pneumonitis, atezolizumab should not be resumed after permanent discontinuation.

23 MAY 2023 Version 6.0 Page: 67 of 181

Immune-mediated hepatitis

Immune-mediated hepatitis, defined as requiring use of corticosteroids and with no clear alternate etiology, occurred in patients receiving atezolizumab treatment. Liver test abnormalities occurred in patients who received atezolizumab. Refer to the latest available version of atezolizumab IB for further details. For management of liver toxicity, refer to the Section 7.4.3.2.2 and Table 7–5.

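### Table 7-6 marks its bar on resuming atezolizumab after pneumonitis only on the Grade 2 line, while its rechallenge footnote is at odds with that bar and with the withdrawal rules of Section 6.4.1.3

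*Protocol*

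**What the plan says.** Section 7.4.3.3 introduces Table 7-6 as the severity-based management of immune-mediated pneumonitis. The table's title and row label are wider and cover pulmonary events in general.

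The table contains two permanent-discontinuation instructions:

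- **Grade 2**, if the event has not come down to Grade 1 or better by 12 weeks. Markers: a, b, c and d.
- **Grade 3 or 4**, immediately: "Permanently discontinue atezolizumab and contact sponsor". Marker: c only.

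Footnote c reads: "Resumption of atezolizumab may be considered in patients who are deriving benefit and have fully recovered from the immune-related event". It adds a condition: "Patients can be rechallenged with atezolizumab only after approval has been documented by both the investigator (or an appropriate delegate) and the sponsor". Footnote d reads: "In case of pneumonitis, atezolizumab should not be resumed after permanent discontinuation".

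Elsewhere in Section 7.4.3.3, the list of reasons for permanent discontinuation includes "Grade 3 or 4 pneumonitis" and does not mention later resumption. The general text on specific adverse events calls for permanent discontinuation after life-threatening immune-mediated events and then continues: "However, resumption of atezolizumab may be considered in patients who are deriving benefit and have fully recovered from the immune-related event". It states no exception for pneumonitis.

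Section 6.4.1.3 lists toxicities for which withdrawal from study treatment is mandatory. Three matter here:

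- any Grade 4 non-hematological toxicity;
- atezolizumab-related non-hematologic toxicity of at least Grade 3 that requires discontinuation;
- atezolizumab-related non-hematologic toxicity of at least Grade 2 that has not resolved to Grade 1 within 12 weeks.

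Section 7.2 defines study treatment as the combination of both drugs.

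**The concern.** An investigator whose patient has recovered from pneumonitis needs to know whether atezolizumab may ever be given again. The protocol gives more than one answer, depending on whether the reader follows the footnote markers, the wording of footnote d, the general text, or the withdrawal section.

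The Grade 3 or 4 line is where the ambiguity matters most. Permanent discontinuation is immediate there, yet the only footnote cited is the one that opens the way to rechallenge. Re-exposure after a serious lung toxicity is a direct safety decision, and pneumonitis is an adverse event of special interest in Section 9.6.1.6.

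**Working it through.** No arithmetic applies. The check sets the passages side by side.

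| Place | Trigger | Is later resumption addressed? |
|---|---|---|
| Table 7-6, Grade 2 line | Unresolved at 12 weeks | c: may be considered; d: no, in case of pneumonitis |
| Table 7-6, Grade 3 or 4 line | The event itself, plus events routed to this column | c: may be considered; d not marked |
| 7.4.3.3, permanent-discontinuation list | Grade 3 or 4 pneumonitis | Silent |
| 7.4.3.3, general text | Life-threatening immune-mediated events | May be considered; no pneumonitis exception |
| 6.4.1.3 | The three triggers above | Mandatory withdrawal; no resumption provision for these triggers |

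1. **Reading by marker.** The lines carry {a, b, c, d} for Grade 2 and {c} for Grade 3 or 4. The explicit bar is therefore attached to unresolved Grade 2 events only.

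2. **Reading by wording.** Footnote d names pneumonitis and has no grade limit, so it covers Grade 3 or 4 as well. It then contradicts c on the Grade 3 or 4 line, and it already sits beside c on the Grade 2 line.

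3. **Whether marker placement carries meaning.** Footnote c is not attached to every permanent-discontinuation line in the section. In Table 7-9 it is on Grade 3 or 4 neuropathy but not on myasthenia gravis and Guillain-Barré syndrome, nor on Grade 2 to 4 myelitis. In Table 7-12 it is absent from Grade 3 or 4 renal events. A site can reasonably take its presence on the Grade 3 or 4 pulmonary line as deliberate.

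4. **Who is reached.** Besides Grade 3 or 4 events, Table 7-6 sends three groups to the same column: recurrent Grade 1 events, recurrent Grade 2 events, and Grade 2 events that do not improve after 48 to 72 hours of steroids.

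5. **Scope of the general sentence.** It follows a statement about life-threatening events. For Grade 3 pneumonitis the permission therefore comes from footnote c alone.

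6. **Section 6.4.1.3.** Atezolizumab-related Grade 3 or 4 pneumonitis requires discontinuation under Section 7.4.3.3 and so triggers mandatory withdrawal; Grade 4 triggers it a second time. Atezolizumab-related Grade 2 pneumonitis unresolved at 12 weeks also triggers it. Where that list intends an exception it says so: the retinal-disorder item provides for resumption after discussion with the sponsor. None of the three items here does, so footnote c and the general sentence are in tension with them. The Grade 3 item refers the reader back to Section 7.4.3.3, where the conflict sits.

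**The case against.** The strongest reply is that c and d fit together. The table covers pulmonary events at large; c is the general rule, repeated almost unchanged under Tables 7-7, 7-8 and 7-10, and d is the pneumonitis exception for all grades. On that reading only a superscript is missing. The reading is possible, but it does not close the point. Section 7.4.3.3 introduces the table as the management of immune-mediated pneumonitis, c refers to an immune-related event, and d is still not marked on the line where discontinuation is immediate.

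A second reply is that footnote c requires documented approval from both investigator and sponsor, so no site can rechallenge on its own reading. That is a real safeguard. It settles who approves, not whether the protocol allows approval.

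A third is extraction. The Grade 3 or 4 column has visibly lost at least one word after its mention of broad-spectrum treatment, so a lost marker cannot be excluded. Both marker strings are legible, however, and a restored d would only place it beside c there too. The tension with Section 6.4.1.3 would remain.

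Two stronger inferences are tempting and not supported:

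- **That the protocol as a whole sets a weaker bar for the more severe event.** Section 6.4.1.3 requires withdrawal in both situations when the event is atezolizumab-related, and for Grade 4 the requirement is repeated in Section 7.4.3.2. The asymmetry lies in the markers of Table 7-6.
- **That the conflict will distort the response rate.** Section 5.2.3 says no further analysis is planned after primary completion, so reconciling the text now would not alter those results.

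**Conclusion.** The point holds as an internal contradiction about re-exposure. Table 7-6 attaches its only explicit bar to the Grade 2 line, the wording of that bar conflicts with footnote c, and both c and the general resumption sentence are in tension with the mandatory withdrawals in Section 6.4.1.3.

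Its size cannot be given as a number. The documents state no pneumonitis rate, and footnote c would in any case reach only patients who are benefiting and have fully recovered. Its relevance is to the safety of patients who remain on treatment under version 6.0. It has no bearing on sample size or on the dose-selection operating characteristics.

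The conclusion assumes that the extracted markers are those printed and, for the atezolizumab-specific triggers in Section 6.4.1.3, that the pneumonitis is judged related to atezolizumab. The conflict of wording between c and d does not depend on either assumption. This should be corrected, because the instructions concern a serious toxicity and the correction is small.

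**What to change.** Reconcile four items together: footnotes c and d of Table 7-6; their markers on the Grade 2 and the Grade 3 or 4 lines; the general resumption sentence in Section 7.4.3.3; and the three withdrawal items in Section 6.4.1.3. The protocol should then state once, for each grade and for the events routed to the Grade 3 or 4 column, whether resumption after permanent discontinuation for pneumonitis is possible, with the other places referring to that statement. If c is meant for pulmonary events other than pneumonitis, it should say so.

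Which rule applies is for the sponsor's medical team; no view is offered here. The cost is footnote markers, a sentence or two and a cross-reference in the next amendment. No analysis changes.

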Immune-mediated colitis or diarrhea

Immune-mediated colitis or diarrhea, defined as requiring use of corticosteroids and with no clear alternate etiology, occurred in patients receiving atezolizumab. Refer to the latest available version of atezolizumab IB for further details. It is recommended to monitor patients for signs and symptoms of diarrhea or colitis.

All events of diarrhea or colitis should be thoroughly evaluated for other more common etiologies including rogaratinib-related gastrointestinal toxicities. For events of significant duration or magnitude or associated with signs of systemic inflammation or acute-phase reactants (e.g., increased CRP, platelet count, or bandemia): perform sigmoidoscopy (or colonoscopy, if appropriate) with colonic biopsy, with three to five specimens for standard paraffin block to check for inflammation and lymphocytic infiltrates to confirm colitis diagnosis.

Management of immune-related colitis will be according to its severity (Table 7–7).

23 MAY 2023 Version 6.0 Page: 68 of 181

Table 7–7: Management guidelines for immune-mediated gastrointestinal events (diarrhea or colitis)

Event	CTCAE Grade 1	CTCAE Grade 2	CTCAE Grade 3 or 4
Diarrhea or colitis	Continue atezolizumab.	Withhold atezolizumab	Grade 3 Withhold atezolizumab
	Initiate symptomatic	Initiate symptomatic treatment.	
	treatment (oral fluids,	If etrang clinical suspicion for	Refer patients to gastrointestinal
	loperamide, avoid high fiber/lactose diet).	If strong clinical suspicion for immune-mediated colitis, start empiric i.v. steroids while	specialist for evaluation and confirmatory biopsy.
	Endoscopy is recommended if	waiting for definitive diagnosis.	Initiate treatment with 1-2 mg/kg/day intravenous
	symptoms persist for >7 days.	Patient referral to gastrointestinal specialist is recommended.	methylprednisolone or equivalent and convert to 1-2 mg/kg/day oral prednisone or equivalent
	Monitor closely.	recommended.	upon improvement. If event does
		For recurrent event or for events that persist >5 days, initiate treatment with 1-2 mg/kg/day oral prednisone or equivalent. If the event does	not improve within 48 hours after initiating corticosteroids, consider adding an immunosuppressive agent.
		not improve within 48 hours after initiating corticosteroids, consider adding an immunosuppressive agent.	Resume atezolizumab if event resolves to ≤ Grade 1 within 12 weeks. ^{a,b}

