	Initiate treatment with anti-thyroid drugs such as methimazole or carbimazole as needed
	Refer to endocrinologist
	Resume atezolizumab when symptoms are controlled and thyroid function is improving
	In case of Grade 4 immune-mediated hyperthyroidism, permanently discontinue atezolizumab and contact the sponsor $^{\rm c}$

23 MAY 2023 Version 6.0 Page: 71 of 181

Table 7–8: Management guidelines for endocrine events

Event	Management
Symptomatic adrenal	Withhold atezolizumab ^a
insufficiency Grade 2-4	Refer patient to endocrinologist
	Perform appropriate imaging
	Initiate treatment with 1–2 mg/kg/day intravenous methylprednisolone or equivalent and convert to 1–2 mg/kg/day oral prednisone or equivalent upon improvement
	Resume atezolizumab if event resolves to Grade 1 or better and patient is stable on replacement therapy (if required) within 12 weeks ^{a, b}
	Permanently discontinue atezolizumab and contact sponsor if event does not resolve to Grade 1 or better or patient is not stable on replacement therapy within 12 weeks $^{\rm a,b,c}$
Hyperglycemia, Grade 1 or 2	Continue atezolizumab
	Initiate treatment with insulin if needed
	Monitor for glucose control
Hyperglycemia, Grade 3 or 4	Withhold atezolizumab
	Initiate treatment with insulin
	Monitor for glucose control
	Resume atezolizumab when symptoms resolve and glucose levels are stable

i.v. = intravenous; mIU = Milli international unit; MRI = magnetic resonance imaging; TSH = thyroid-stimulating hormone.
 a: If corticosteroids have been initiated, they must be tapered over ≥ 1 month to ≤ 10 mg/day oral prednisone or equivalent before atezolizumab can be resumed.

Severe cutaneous adverse reactions

Severe cutaneous adverse reactions are an identified risk of atezolizumab. Severe cutaneous adverse reactions are a heterogeneous group of immunologically mediated drug eruptions frequently associated with drug use including immune checkpoint inhibitors as a class. Although rare, these events are potentially fatal, and mainly constituted by erythema multiforme, acute generalised exanthematous pustulosis, SJS, TEN, and drug rash with eosinophilia and systemic symptoms.

The management of severe cutaneous adverse reactions will be as follows:

 For suspected severe cutaneous adverse reactions, refer patients to a dermatologist for further diagnosis and management

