myositis, Grade 1	Refer patient to rheumatologist or neurologist.								
	Initiate treatment as per institutional guidelines.								
Immune-related	Withhold atezolizumab for up to 12 weeks after event onset ^a and contact sponsor.								
myositis, Grade 2	Refer patient to rheumatologist or neurologist.								
	Initiate treatment as per institutional guidelines.								
	Consider treatment with corticosteroid equivalent to 1-2 mg/kg/day i.v. methylprednisolone and convert to 1-2 mg/kg/day oral prednisone or equivalent upon improvement.								
	If corticosteroids are initiated and event does not improve within 48 hours after initiating corticosteroids, consider adding an immunosuppressive agent.								
	If event resolves to Grade 1 or better, resume atezolizumab. b								
	If event does not resolve to Grade 1 or better while withholding atezolizumab, permanently discontinue atezolizumab and contact sponsor. c								
Immune-related	Withhold atezolizumab for up to 1 weeks after event onset ^a and contact sponsor.								
myositis, Grade 3	Refer patient to rheumatologist or neurologist.								
	Initiate treatment as per institutional guidelines.								
	Respiratory support may be required in more severe cases.								
	Initiate treatment with corticosteroids equivalent to 1-2 mg/kg/day i.v. methylprednisolone or higher-dose bolus if patient is severely compromised (e.g. cardiac or respiratory symptoms, dysphagia, or weakness that severely limits mobility); convert to 1-2 mg/kg/day oral prednisolone or equivalent upon improvement.								
	If event does not improve within 48 hours after initiating corticosteroids, consider adding an immunosuppressive agent.								
	If event resolves to Grade 1 or better, resume atezolizumab. ^b								
	If event does not resolve to Grade 1 or better while withholding atezolizumab, permanently discontinue atezolizumab and contact sponsor. c								
	For recurrent events, treat as a Grade 4 event.								
Immune-related	Permanently discontinue atezolizumab and contact sponsor. c								
myositis, Grade 4	Refer patient to rheumatologist or neurologist.								
	Initiate treatment as per institutional guidelines. Respiratory support may be required in more severe cases.								

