	Initiate treatment with corticosteroids equivalent to 1-2 mg/kg/day i.v. methylprednisolone or higher-dose bolus if patient is severely compromised (e.g. cardiac or respiratory symptoms, dysphagia, or weakness that severely limiting mobility); convert to 1-2 mg/kg/day oral prednisone or equivalent upon improvement.								
	If event does not improve within 48 hours after initiating corticosteroids, consider adding an immunosuppressive agent.								

23 MAY 2023 Version 6.0 Page: 79 of 181

Table 7–13: Management guidelines for immune-related myositis

Event	Management
	If event resolves to Grade 1 or better, taper corticosteroids over ≥ 1 month.

i.v. = intravenous

- a: Atezolizumab may be withheld for a longer period of time (i.e., > 12 weeks after event onset) to allow for corticosteroids (if initiated) to be reduced to ≤ 10 mg/day oral prednisone or equivalent. The acceptable length of the extended period of time must be agreed upon by the investigator and the sponsor.
- b: If corticosteroids have been initiated, they must be tapered over ≥ 1 month to ≤ 10 mg/day oral prednisone or equivalent before atezolizumab can be resumed.
- c: Resumption of atezolizumab may be considered in patients who are deriving benefit and have fully recovered from the immune-related event. Patients can be re-challenged with atezolizumab only after approval has been documented by both the investigator (or an appropriate delegate) and the sponsor.

Systemic immune activation

Systemic immune activation (SIA) is a rare condition characterized by an excessive immune response. Given the mechanism of action of atezolizumab, SIA is considered a potential risk when given in combination with other immunomodulating agents. SIA should be included in the differential diagnosis for patients who, in absence of an alternate etiology, develop a sepsis-like syndrome after administration of atezolizumab.

Recommendations regarding early identification of SIA are provided below. In event of suspected SIA, the sponsor should be contacted immediately for additional guidance and study treatment should be interrupted. At ezolizumab should be permanently discontinued in patients with life-threatening immune-mediated adverse events.

Early disease recognition is critical, and the clinician should consider SIA if, in absence of alternative etiologies, ≥ 2 of the following are present:

- Hypotension refractory to aggressive i.v. fluid challenge. May/can require vasopressin support

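### Table 7-13 prints a one-week limit on the atezolizumab hold for Grade 3 myositis, which the row's own steroid-taper and extension footnotes make unworkable; 12 weeks looks intended

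*Protocol*

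**What the plan says.** Protocol Section 7.4.3.3, Table 7-13, sets out the management of immune-related myositis by grade.

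- **Grade 3, hold limit:** "Withhold atezolizumab for up to 1 weeks after event onset", with footnote a attached and an instruction to contact the sponsor.
- **Grade 3, steroids:** "Initiate treatment with corticosteroids equivalent to 1-2 mg/kg/day i.v. methylprednisolone or higher-dose bolus if patient is severely compromised".
- **Grade 3, resumption:** atezolizumab restarts once the event is at Grade 1 or better, subject to footnote b.
- **Grade 3, failure to resolve:** "If event does not resolve to Grade 1 or better while withholding atezolizumab, permanently discontinue atezolizumab and contact sponsor", subject to footnote c, which allows rechallenge after full recovery with documented approval.
- **Grade 2, hold limit:** "Withhold atezolizumab for up to 12 weeks after event onset", also with footnote a.
- **Footnote a:** "Atezolizumab may be withheld for a longer period of time (i.e., > 12 weeks after event onset"), to allow steroids to be reduced, for a length agreed between investigator and sponsor.
- **Footnote b:** if steroids have been started, "they must be tapered over ≥ 1 month to ≤ 10 mg/day oral prednisone or equivalent before atezolizumab can be resumed".

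Elsewhere, the withhold list in Section 7.4.3.3 puts Grade 2 and Grade 3 myositis in one entry with no separate time limit. Section 6.4.1.3 withdraws a patient whose atezolizumab-related non-hematologic toxicity of Grade 2 or higher has not come down to Grade 1 within 12 weeks. Both sections also set a general maximum hold of 42 days past the next due dose, with an exception for steroid tapering.

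**The concern.** The hold limit decides when a patient loses atezolizumab for good, because an event that has not settled during the hold leads to permanent discontinuation. With a 7-day limit, the same row tells the site to give steroids, to taper them over at least a month before restarting, and to end the hold within a week. These instructions cannot all be obeyed.

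A site could err in either direction. It could stop the drug at day 7 in a patient who would have recovered, or it could take the one-week figure as leave to re-dose early in a potentially severe event. Version 6.0 is the current protocol, so this is a live treatment instruction. The plural noun after the figure 1 suggests a dropped digit.

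**Working it through.** The plan gives no derivation for the one-week figure, so the check is whether it can stand beside the rest of the row and, if not, which value the documents support.

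**Inputs**

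| Item | Value | Source |
|---|---|---|
| Grade 3 hold limit as printed | 1 week = 7 days | Table 7-13 |
| Minimum steroid taper before resuming | 1 month, taken as 28 to 31 days | Table 7-13, footnote b |
| Point beyond which a hold counts as longer | 12 weeks = 84 days | Table 7-13, footnote a |
| Infusion interval | 21 days | Section 7.4.1.2 |
| General maximum hold | 42 days past the next due dose | Sections 6.4.1.3 and 7.4.3.3 |

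**Step 1: taper against hold.** The Grade 3 row directs steroids, so footnote b applies whenever the row is followed. The ratio is 28/7 = 4.0 to 31/7 = 4.4. Even a patient at Grade 1 by day 7 could not restart within the printed limit, so the resume line can never be used inside it.

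**Step 2: footnote a against hold.** With a base limit of 7 days and an extension worded as more than 84 days, days 8 to 84 fall under neither. With a base limit of 84 days the gap disappears.

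**Step 3: does a 7-day hold withhold anything?** For onset d days after an infusion (d = 0 to 20), the hold ends on day d + 7 and the next infusion is due on day 21. If d + 7 < 21, that is d = 0 to 13, the hold is over before any dose falls due. That covers 14 of the 21 possible onset days.

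**Step 4: which value is supported?**
- The same sentence appears in four other cells: hypophysitis Grade 2 or 3 (Table 7-8), neuropathy Grade 2 (Table 7-9), renal event Grade 2 (Table 7-12) and myositis Grade 2 (Table 7-13). All four read 12 weeks.
- Rows for other events that cover Grade 3 and set a time for resuming also use 12 weeks. For diarrhea or colitis (Table 7-7): "Resume atezolizumab if event resolves to ≤ Grade 1 within 12 weeks". For adrenal insufficiency (Table 7-8): "Resume atezolizumab if event resolves to Grade 1 or better and patient is stable on replacement therapy (if required) within 12 weeks". The hypophysitis row and the amylase/lipase and pancreatitis rows of Table 7-10 agree.
- The withdrawal criterion in Section 6.4.1.3 uses 12 weeks, and the withhold list in Section 7.4.3.3 does not separate Grade 3 myositis from Grade 2.
- No part of the protocol supports one week.

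**Step 5: does 12 weeks fit?** A taper of 28 to 31 days fits within 84 days, leaving 84 − 31 = 53 to 84 − 28 = 56 days. Measured from onset, the general maximum is (21 − d) + 42, which is 43 days (d = 20) to 63 days (d = 0). A full 84-day hold exceeds this by 21 to 41 days. Because the row directs steroids, the steroid-taper exception in Section 7.4.3.3 can cover the excess by agreement between investigator and sponsor.

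**The case against.** The strongest objection is that the protocol itself may contain no error. The text examined was extracted from a PDF, and neighboring tables show real losses: a noun is missing after the broad-spectrum treatment in Table 7-6, a taper duration is missing from the Grade 4 cell of Table 7-7, and Table 7-11 cites footnotes that do not appear. A dropped 2 would look exactly like this. The four other copies came through intact, but that does not prove this one did. This objection stands and makes the point conditional on the source PDF.

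Two stronger readings are tempting, and the documents do not support either:

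- **That the gap between Grade 2 (84 days) and Grade 3 (7 days) is itself a contradiction.** A stricter rule at Grade 3 is ordinary in this protocol: pneumonitis, neuropathy and renal events are withheld at Grade 2 and stopped permanently at Grade 3. The agreement among Grade 3 rows in Step 4 is confined to rows that allow resumption, so it supports the value 12 but does not rule out a stricter limit.
- **That 7 days contradicts the 42-day general limit.** A specific limit shorter than a general maximum is compatible with it.

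It is also fair to say that footnote a gives a threshold for an extended hold and does not state the base limit. It presupposes about 12 weeks without saying so. The firm conflict is with footnote b.

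Finally, a site reading the whole protocol would probably not discontinue at day 7 unprompted. Sponsor contact is required, footnote a is open to every patient on steroids, and footnote c allows rechallenge. This limits the harm but does not make the cell correct.

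**Conclusion.** As printed, the Grade 3 cell of Table 7-13 cannot be reconciled with its own footnotes. A mandatory taper of at least 28 to 31 days does not fit in 7 days, and the extension wording leaves days 8 to 84 uncovered. Twelve weeks is the value that the rest of the protocol supports. This rests on two assumptions: that the source PDF really prints one week, which is unconfirmed, and that a month means 28 to 31 days.

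The consequence is small. Only patients still on treatment who develop Grade 3 myositis are affected. Section 5.2.3 plans no further analysis after primary completion. A reader might infer that the MTD or an endpoint is at risk, but the documents do not support that. Under Section 7.4.3.1 a drug-related Grade 3 myositis in Cycle 1 is already a DLT whatever the hold length, and no endpoint definition or analysis set refers to this row. It is a one-cell correction to a safety table, worth making because the cell governs permanent discontinuation.

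**What to change.** 1. Check the Grade 3 cell of Table 7-13 in the source PDF. If it reads 12 weeks, nothing needs to change.
2. If it reads one week, confirm the intended limit in the atezolizumab investigator's brochure, to which Amendment 4 aligned these guidelines. Then change the cell to a hold of up to 12 weeks and keep footnotes a, b and c.
3. No change to the general 42-day rule is needed. A hold that runs past it is covered by the existing steroid-taper exception in Section 7.4.3.3.

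The cost is one table cell, in a clarification letter to sites or the next amendment. Data collection, the SAP and the planned outputs are untouched.
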